# Study Information

## Title

Heart Transplant Tradeoff Study: 5-Condition Layperson Study

## Authors

## Description

Publicly available outcome assessments for transplant programs do not make salient that some programs tend to reject many of the hearts they are offered, whereas other programs accept a broader range of donor offers. We use empirical studies to test whether transplant center performance data (i.e. transplant and waitlist outcome statistics) that reflect center donor acceptance rates influence laypersons to evaluate centers with high organ decline rates less favorably than centers with low organ decline rates. 1000 lay participants will be recruited from Amazon Mechanical Turk and randomized to one of five different information presentation conditions. Participants will be given an introduction to the donor organ match process, then asked to view the table of transplant outcomes corresponding to the condition they were randomized to. Each participant is asked to choose between two hospitals: one hospital with a non-selective, "accepting" strategy (takes all donor heart offers), and one hospital with a more selective, "cherrypicking" strategy (tends to reject donor offers that are less than "excellent" quality). In order to identify the decision process that underlies this choice pattern, we will examine a putative mediator. Specifically, participants will be asked to rate the extent to which they considered patients' chances of getting an excellent heart, avoiding a less-than-optimal heart, and getting any type of heart when making their choice between the two hospitals.

## Hypotheses

Hypothesis 1: When centers must present information on their transplant success rate only, lay evaluators will respond by selecting hospitals with higher transplant success. However, if information presented on transplant outcomes is stratified by the number and quality of donors used, or displayed in addition to total survival rates, then participants will respond by selecting hospitals with higher organ acceptance rates rather than the hospital with higher transplant outcomes. Hypothesis 1a: Preference for the non-selective transplant center will be lower (than for the selective center) in condition 1 (baseline: combined transplant survival only), compared to the other 4 conditions. That is, a higher proportion of participants will prefer the non-selective center over the selective center in conditions 2, 3, 4, and 5, relative to condition 1. Hypothesis 1b: There will be a main effect of viewing total survival, such that in conditions 2 and 4 (when total survival is displayed), participants will prefer the non-selective center over the selective center, relative to the baseline condition 1. Hypothesis 1c: There will be an additional main effect of viewing stratified transplant survival, such that in conditions 3 and 4 (when transplant survival is stratified by number and quality of donor hearts accepted at each center) participants will prefer the non-selective center over the selective center, relative to the baseline condition 1. Hypothesis 1d: There will be an interaction effect between total and stratified transplant survival, such that when participants view both stratified transplant survival and total survival outcomes together, preference for the non-selective center is higher relative to preferences at baseline (condition 1), but not higher relative to preferences when total survival information is added to the display (condition 2) or stratified transplant survival

only is displayed (condition 3). Hypothesis 2: There will be an indirect (mediated) effect of providing participants with information about stratified transplant survival or total survival; this information will lead to higher preference for the non-selective hospital by leading participants to think that the chances a patient at either hospital will "get a heart at all" is a more important factor in their decision (about which hospital is a better choice for patients). Specifically ratings of importance (0-100 continuous scale) for the item "likelihood of getting any heart" will differ across conditions 1-4 such that "getting any heart" will be rated lower in condition 1 than in the other three conditions. Furthermore, ratings on this item will be associated with choice, such that higher ratings will be associated with choice of the non-selective center. Hypothesis 3: Participants who view total survival only (condition 5) will show a higher preference for the non-selective center relative to participants in the baseline combined transplant survival display (condition 1) such that the effect of displayed total survival alone will be similar to the effect of displaying both stratified transplant survival and total survival outcomes together (as in condition 4).

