### Study design

We have a between-subjects design in which participants are randomized to one of five information conditions. In each condition, they make a choice between two hospitals (one with a non-selective donor acceptance strategy, and another with a more selective donor acceptance strategy). The first four conditions (1-4) will be included in our main analysis, which is a 2x2 design with 2 factors (total survival and transplant survival) and 2 levels per factor: (i) Total survival: "total not displayed" = reference level, in which only transplant survival rate (and not total or waitlist survival) is shown "total displayed" = transplant survival is displayed along with the overall survival rate at each center, which is computed from survival rates of both transplant and waitlist patients (ii) Transplant survival: "combined": reference level, in which transplant survival rate is not stratified by number and quality of donor hearts accepted at each center "stratified": transplant survival rate stratified into patients who received excellent donor organs and patients who received less than optimal donor organs The additional fifth condition, in which only total survival outcomes (and no transplant survival outcomes) are displayed, will be included in the study and analyzed separately.

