### Sample size rationale

Sample sizes were calculated to yield at least 90% power to detect a 15 percentage point difference (e.g., 45% vs. 60%) between baseline condition 1 and the other 4 conditions, with  $\alpha=0.05$  (GPower 3.1.9.4).

Stopping rule

Participants will be recruited until a sample size of 1000 is achieved.

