## Analysis Plan

Statistical models

To test Hypotheses 1a /1b/1c/1d, we will use a binomial logistic regression analysis. The two categorical independent variables will be 'total survival displayed' and 'stratified transplant survival'; the model will also include an interaction term of these two variables. The dependent variable is binary choice of hospital. -We will test whether the main effect of "total survival displayed" is statistically significant and in the predicted positive direction. -We will test whether the main effect of "stratified transplant survival" is statistically significant and in the predicted positive direction. -We will test whether the interaction effect "total\*stratified" is statistically significant in the predicted negative direction. To test Hypothesis 2, we will conduct a causal mediation analysis to determine whether information display had a mechanistic effect on hospital choice through our proposed mediator. We will estimate the average causal mediation effect (ACME), average direct effect (ADE), and the total effect. The ACME is the effect of each information display condition (total, stratified, or total\*stratified) on the outcome of hospital choice (selective vs. non-selective), mediated through the hypothesized mediator (the importance of "getting any heart" at each hospital when considering the choice). The remaining effect of information display on hospital choice that is not mediated through the hypothesized mediator represents the ADE. The entire effect of the information display on hospital choice via the hypothesized mediator and the direct effect is the total effect. The proportion of the total effect that is accounted for by the ACME is called the proportion mediated.{Imai, 2010}. Analyses will be performed using the "mediation" package in R (The R Foundation for Statistical Computing).{Tingley, 2014}. We will generate 95% confidence intervals by using 1000 bootstrap simulations. The unstandardized point estimate of the ACME and its 95% confidence intervals will be interpreted. -A significant ACME for "total survival displayed" would suggest that displaying total survival works via increasing the perceived importance of "getting any heart" to increase preference for the non-selective hospital. If the ACME is non-significant, we will identify where the causal path breaks down. -A significant ACME for "stratified transplant survival" would suggest that stratifying transplant survival by number and quality of accepted donors works via increasing the perceived importance of "getting any heart" to increase preference for the non-selective hospital. If the ACME is non-significant, we will identify where the causal path breaks down. -A significant ACME for "total survival displayed\*stratified transplant survival" would suggest that the combination of displaying total survival and stratifying transplant survival by number and quality of accepted donors works via increasing the perceived

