
importance of "getting any heart" to increase preference for the non-selective hospital. If the ACME is non-significant, we will identify where the causal path breaks down. To test Hypothesis 3, we will use a binomial logistic regression analysis with a contrast test for a difference in effect size between conditions 4 and 5.

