#### *No files selected*

##### Transformations

Logistic regression analysis: The categorical predictor "total survival displayed" will be dummy coded (0=not displayed, 1=displayed), with 'not displayed' as the reference category. The categorical predictor "transplant survival stratified" will be dummy coded (0=not stratified, 1=stratified), with 'stratified' as the reference category. The outcome variable "choice of hospital" will be dummy-coded (0=selective hospital, 1=non-selective hospital). The reference category is 'selective hospital'. Mediation analysis: The categorical predictor "total survival displayed" will be dummy coded (0=not displayed, 1=displayed), with 'not displayed' as the reference category. The categorical predictor "transplant survival stratified" will be dummy coded (0=not stratified, 1=stratified), with 'stratified' as the reference category. The categorical interaction term "total survival displayed\*transplant survival stratified" will be dummy coded (0=total and stratified information not displayed together, 1=both total and stratified information displayed together), with 'both' as the reference category. The continuous mediator variable "get any heart" will be mean-centered for each analysis. The outcome variable "choice of hospital" will be dummy-coded (0=selective hospital, 1=non-selective hospital). The reference category is 'selective hospital'.

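### The negative-interaction test planned for Hypothesis 1d shows sub-additivity; it does not show that condition 4 is no higher than conditions 2 and 3

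*Combined protocol and SAP*

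**What the plan says.** Under Hypotheses, H1d opens by predicting an interaction between the two display factors and then gives its shape. Preference for the non-selective center in condition 4 is higher than in condition 1, "but not higher relative to preferences when total survival information is added to the display" (condition 2), and not higher than when stratified transplant survival "only is displayed (condition 3").

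The Analysis Plan (Statistical models) covers H1a to H1d with one binomial logistic regression on conditions 1 to 4. It has two binary factors, and "the model will also include an interaction term of these two variables". Three coefficients are tested: each factor for a positive sign, and the interaction for whether it "is statistically significant in the predicted negative direction". Only the last bears on H1d. The one contrast that names condition 4 belongs to H3: a "contrast test for a difference in effect size between conditions 4 and 5". Inference criteria gives a p=0.05 difference rule and nothing for a conclusion of no excess. Sample size rationale powers condition 1 against the other conditions, with 45% vs 60% as its example.

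**The concern.** With combined survival and total not displayed as reference levels (Study design), the two single-factor coefficients compare 2 with 1 and 3 with 1. The interaction is a difference between log-odds differences. None of the three tests compares condition 4 with condition 2 or 3, yet that comparison is what gives H1d its content: does showing both displays add anything over showing one?

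Two errors are possible. A significant negative interaction can be taken as support for H1d when condition 4 is in fact above both 2 and 3. A non-significant one can count against H1d when it is true. If the 4 vs 2 and 4 vs 3 contrasts are not named in advance, looking at them later is post hoc.

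**Working it through.** **Inputs.** About 200 per condition (Sample size); 45% and 60% as example rates and alpha 0.05 (Sample size rationale); the 2x2 logistic model (Statistical models). All other rates below are assumptions. Tests are two-sided at 0.05, also an assumption because the plan does not state sidedness.

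**The plan's own figure.** For 45% vs 60%, pooled-variance normal approximation, 200 vs 200: null SE = sqrt(2 × 0.525 × 0.475/200) = 0.0499; alternative SE = sqrt((0.45 × 0.55 + 0.60 × 0.40)/200) = 0.0494. Two-sided power = Φ((0.15 − 1.96 × 0.0499)/0.0494) = 85.4%; one-sided 91.5%; 200 vs 800 pooled, two-sided, 96.9%. The stated 90% is therefore reached on a one-sided or pooled reading. On no reading does it concern the interaction, 4 vs 2 or 4 vs 3.

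**What the coefficient measures.** b = logit(p4) − logit(p2) − logit(p3) + logit(p1). So b < 0 means logit(p4) − logit(p2) < logit(p3) − logit(p1). This does not imply p4 ≤ p2 or p4 ≤ p3.

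**Additive benchmark at 45/60/60.** logit(0.60) = 0.405 and logit(0.45) = −0.201, so additivity gives logit(p4) = 2 × 0.405 + 0.201 = 1.01 and p4 = 73.3%. Any true p4 below 73.3% gives a negative interaction, including values up to 13.3 points above conditions 2 and 3.

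**How often the planned test succeeds.** SE(b) = sqrt(Σ 1/(200·p·q)); chance of a significant negative result ≈ Φ(|b|/SE − 1.96) for b < 0, confirmed with 200,000 simulated trials per scenario.

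| True rates, conditions 1/2/3/4 (%) | b | SE | Negative interaction significant | and condition 4 significantly above both 2 and 3 |
|---|---|---|---|---|
| 45/60/60/60 (H1d exactly true) | −0.606 | 0.288 | 56% | 0% |
| 45/60/60/70 | −0.164 | 0.293 | 8% | under 0.1% |
| 45/75/75/85 | −0.663 | 0.336 | 50% | 13% |
| 30/60/60/70 | −0.811 | 0.299 | 78% | 20% |
| 20/60/60/75 | −1.099 | 0.316 | 94% | 77% |

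The 30/60/60/70 row by hand: b = 0.847 − 0.405 − 0.405 − 0.847 = −0.811; SE = sqrt(2/42 + 2/48) = 0.299; z = −2.71.

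**Precision of the direct comparison.** At 60% in both arms, SE = sqrt(2 × 0.24/200) = 0.049, so the 95% interval is ±1.96 × 0.049 = ±9.6 points. With no true difference, its upper limit falls below 10 points with probability Φ(0.10/0.049 − 1.96) ≈ 53% for one contrast.

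**The case against.** The strongest defence has four parts.

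- **H1d leads with an interaction claim, and that claim is tested.** This stands. What has no test is the described shape, not the whole hypothesis.
- **The contrasts can be recovered.** This also stands. The model is saturated, so on the log-odds scale 4 vs 2 is the stratified plus the interaction coefficient, and 4 vs 3 is the total plus the interaction coefficient. The gap is that the plan does not name or interpret them.
- **False support needs large single-display effects.** Correct. A reader might infer from the 78% that the test usually misleads. The documents do not support that: with their 45% and 60% and the same 10-point excess, it is about 8%.
- **The plan never says a significant interaction will be read as no added benefit.** True. A reader might infer such reporting, but Statistical models states only significance and sign.

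A reader might also infer that direct contrasts are always the more powerful way to show H1d. That depends on an assumed margin. At 45/60/60/60, one-sided 95% upper bounds for both contrasts fall below 15 points in 86% of trials but below 10 points in 49%, against 56% for the interaction test.

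The coding text does not close the gap. Study design makes combined survival the "reference level, in which transplant survival rate is not stratified by number and quality of donor hearts accepted at each center", whereas Transformations has "0=not stratified, 1=stratified), with 'stratified' as the reference category". If stratified really were the reference, the total coefficient would become 4 vs 3, but its predicted positive sign would contradict H1d, the interaction sign would flip, and 4 vs 2 would still be untested. The two sections need reconciling.

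**Conclusion.** The concern holds in a limited form. The rule given for H1d answers whether the displays combine less than additively on the log-odds scale; H1d also asks whether condition 4 is no higher than conditions 2 and 3. That mismatch is algebraic and needs no assumption.

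Its practical size does depend on the rates: about 78% false support at 30/60/60/70 (assumed, outside the plan's example) and about 8% at 45/60/60/70. When the pattern is exactly true at 45/60/60/60, the test detects an interaction in only about 56% of trials. These figures assume 200 analysed per condition and two-sided 0.05; exclusions for nonsense answers or incomplete surveys would lower the numbers analysed if they are not replaced.

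It is tempting to take the plan's 15-point difference as a ready-made margin for no excess. The documents do not offer it as one, and it is too wide: full additivity at 45/60/60 gives an excess of only 13.3 points, so fully additive displays could pass.

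**What to change.** In Statistical models, prespecify three contrasts from the same fitted model, expressed as differences in proportions with 95% confidence intervals: 4 vs 1, 4 vs 2 and 4 vs 3. Base any statement that condition 4 is not higher on the 4 vs 2 and 4 vs 3 intervals. Keep the interaction test and describe it only as evidence of sub-additivity. Alternatively, reword H1d as less than additive on the log-odds scale.

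If the sponsor wants a formal conclusion of no excess, it should fix and justify its own margin before data collection; 15 points should not be used. State which level of transplant survival is the reference, consistently in Study design and Transformations.

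The cost is a few lines of text and three contrasts from a model already planned. The downside is precision: with half-widths of about 9.6 points for 4 vs 2 and 4 vs 3, the intervals may not exclude a modest excess. As an illustration, 90% power to exclude 10 points on one contrast at one-sided 0.025 would need 2 × 0.24 × (1.96 + 1.28)²/0.10² ≈ 505 per condition. Reporting the intervals without a margin needs no extra participants.

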## Design Plan

### Study type

Experiment - A researcher randomly assigns treatments to study subjects, this includes field or lab experiments. This is also known as an intervention experiment and includes randomized controlled trials.

### Blinding

- For studies that involve human subjects, they will not know the treatment group to which they have been assigned.

Is there any additional blinding in this study?

n/a

### Study design

We have a between-subjects design in which participants are randomized to one of five information conditions. In each condition, they make a choice between two hospitals (one with a non-selective donor acceptance strategy, and another with a more selective donor acceptance strategy). The first four conditions (1-4) will be included in our main analysis, which is a 2x2 design with 2 factors (total survival and transplant survival) and 2 levels per factor: (i) Total survival: "total not displayed" = reference level, in which only transplant survival rate (and not total or waitlist survival) is shown "total displayed" = transplant survival is displayed along with the overall survival rate at each center, which is computed from survival rates of both transplant and waitlist patients (ii) Transplant survival: "combined": reference level, in which transplant survival rate is not stratified by number and quality of donor hearts accepted at each center "stratified": transplant survival rate stratified into patients who received excellent donor organs and patients who received less than optimal donor organs The additional fifth condition, in which only total survival outcomes (and no transplant survival outcomes) are displayed, will be included in the study and analyzed separately.

### Randomization

We will use simple randomization, where each participant will be randomly assigned to one of the five predetermined conditions. The Qualtrics randomizer function will be used for randomization into a condition.

## Sampling Plan

### Existing Data

Registration prior to creation of data  
Explanation of existing data

n/a

### Data collection procedures

Recruitment: 1000 lay participants will be recruited from Amazon Mechanical Turk, an online crowdsourcing platform used for testing human intelligence tasks and research paradigms. Participants will be recruited via a "HIT" post titled "Healthcare Study (~10 minutes)" described as "choosing between heart transplant hospitals based on outcome data (Potential \$0.20 bonus)." They will be recruited for the HIT upon meeting two criteria. (1) 99% HIT approval rate or higher (2) 1000 or more HITS approved  
Inclusion criteria: Participants who are already qualified mTurk workers with Worker Accounts meeting the above criteria will be asked to participate if they confirm the following inclusion criteria in the consent form. (1) 18 years of age or older (2) must read and understand the information in the consent form (3) must want to participate in the research and continue with the survey (4) must live in United States

Payment: Participants will be paid \$1.33 for completing the survey (raised to \$1.43 if one bonus question is answered correctly and \$1.53 if two bonus questions are answered correctly).

Exclusion criteria: (1) Participants on mTurk will not be allowed to participate if they fail to pass the initial "bot screening", a multiple-choice question that asks, "What phone number should you dial when there is an emergency?" The obvious correct response in this screening question is "911", so participants who select one of the incorrect responses (i.e. "1-800-ANTIBOT", "1-877-MTURKER", "123") are filtered out and not allowed to complete the survey. (2) Participants on mTurk will be allowed to participate, but excluded from data analysis, if they submit a nonsense response to the free-response question which reads, "In your own words, why do you think patients should choose the hospital you picked?" This question takes place after the participant has viewed the choice stimuli and selected their response. If participants input nonsense in the text response box, they will be permitted to complete the survey and paid, but filtered out from the data analysis

### Sample size

Our target sample size is 1000 participants. We expect that this will amount to approximately 200 participants per condition, although due to the nature of the randomization technique used (Qualtrics randomizer function), we may end up with slightly more or slightly less than 200 per condition.

